Using the following equation to calculate sample size for proportional outcomes in randomized controlled trials and using data from a 2012 study by Paul et. al. citing a 58% overall compliance with PALS severe sepsis target times:

$$m \text{ (size per group)} = c \times \frac{\pi_1(1 - \pi_1) + \pi_2(1 - \pi_2)}{(\pi_1 - \pi_2)^2}$$

where c is set at 7.9 for a power of 80%

π_1 is current percent success rate on standard protocol

π_2 is the current percent success plus the anticipated treatment effect percent

We have calculated the total number of subjects in the sepsis arm to be: 82 per group or 164 total patients for a power of 80% and a type I error set at 5%

For the gastroenteritis and dehydration arm we have established a sample size using the following power calculation for continuous (time) outcomes

	Protocol Name:	Randomized Controlled Trial of Inferior Vena Cava Ultrasonography in the Management and Disposition of Pediatric Patients Undergoing Evaluation for Sepsis and Dehydration
	Principal Investigator:	[name] [contact] [contact] or [contact]
	Primary Contact Name/Contact Info:	[name] [contact]
	Date Revised:	2/10/2015
	Study Number:	IF1733382

$$\text{Total sample size} = \frac{c}{\delta^2} + 2$$

where c is set at 7.9 for a power of 80%

δ^2 is set for a 10% size treatment effect (reduction in time)

We would need 200 subjects per group or a total of 400 patients in the gastroenteritis arm of the study.

d) Study Timelines

Currently the Mount Sinai Pediatric Emergency Department sees approximately 30,500 patients on an annual basis. Of this total census about 200 trigger the Stop Sepsis alert upon registration. Based on this we have set the enrollment period over 12 months.

Current census data predicts approximately 3000 Mount Sinai annual emergency department visits for vomiting and dehydration requiring antiemetic therapy. In order to collect a convenience sample of 400 patients and adjust for seasonal variability, the study period will enroll over a six month period between June 2015 and November 2015.

e) Study Endpoints

For the Sepsis arm endpoints include:

Primary

- Secured second vascular access point- type (IO, second IV, CV access) within 15 min of physician evaluation
- Inotrope/Vasopressor use
- Antibiotic within 60 min

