	Protocol Name:	Randomized Controlled Trial of Inferior Vena Cava Ultrasonography in the Management and Disposition of Pediatric Patients Undergoing Evaluation for Sepsis and Dehydration
	Principal Investigator:	[name] [contact] [contact] or [contact]
	Primary Contact Name/Contact Info:	[name] [contact]
	Date Revised:	2/10/2015
	Study Number:	IF1733382

- 60 ml/kg Normal Saline bolus administered within 60 minutes

Secondary

- Disposition- PICU, Floor, Discharge
- Length of ED stay (from sepsis alert to admission/discharge order entry)
- Return ED Visit for same illness
- Survival to hospital discharge
- 30 day mortality
- Left ventricular function
- Source of sepsis

For the Gastroenteritis/Dehydration arm endpoints include:

Primary

- Type of rehydration: oral versus intravenous
- Total amount of fluids given (ml amount)
- Total ED length of stay from triage time to disposition time (order to admit/discharge)

f) Procedures Involved in the Human Research

Allocation of patients to intervention and control arms will be accomplished by a computer generated randomization application Sherlock MD®. Randomization will be separate for sepsis cohort and gastroenteritis cohort. Within sepsis and gastroenteritis cohorts, subjects will be stratified by disease severity. Specifically they will meet criteria for severe sepsis or meet criteria for severe dehydration based on standard clinical severity scoring (e.g. SIRS criteria, Clinical Dehydration Score).

Subjects randomized to either arm will receive diagnostic imaging of the inferior vena cava with ultrasound. Subjects randomized to the investigational arm will undergo IVC ultrasound immediately

	Protocol Name:	Randomized Controlled Trial of Inferior Vena Cava Ultrasonography in the Management and Disposition of Pediatric Patients Undergoing Evaluation for Sepsis and Dehydration
	Principal Investigator:	[name] [contact] [contact] or [contact]
	Primary Contact Name/Contact Info:	[name] [contact]
	Date Revised:	2/10/2015
	Study Number:	IF1733382

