## Gastroenteritis Statistical Plan

We calculated the sample size required to provide more than 80% power (with a two-sided alpha level of 0.05) to detect an absolute difference of 15% in PO vs. IV rehydration or more between groups. We estimated a sample size of 200 patients for the gastroenteritis section of the study.

Enrolled Patients are to be randomized to immediate versus delayed US assessment of the IVC in patients aged 0-21 years who presented to an emergency department with vomiting requiring ondansetron or with diarrhea possibly requiring IV rehydration. Patients enrolled were randomized to assessment of dehydration by clinical exam plus US (immediate) or clinical exam alone and then US 15 minutes later (delayed). Clinical dehydration scores were recorded prior to IVC US. Decision to treat with IV versus PO rehydration, pre-test and post-test probabilities were recorded before and after US. Primary outcomes included IV versus PO rehydration based on intent-to treat principle; secondary outcomes included median total ED length of stay (EDLOS; triage time to disposition) time failure of PO rehydration, and disposition (ED discharge vs admission). All outcomes between groups were compared by using a Pearson chi-squared test. The alpha level was set at .05 for all analyses, 95% CIs were calculated, and all comparisons were two tailed. Data analysis was performed with the use of SPSS 20.0 (IBM).

We calculated the sample size required to provide more than 80% power (with a two-sided alpha level of 0.05) to detect an absolute difference of 15% more more between arms in the number of patients receiving antibiotics with 60 minutes between groups. We estimated a sample size of 200 patients for the sepsis section of the study.

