## Sepsis Statistical Plan

Enrolled Patients are to be randomized to immediate versus delayed US assessment of the IVC in patients aged 0-21 years who presented to an emergency department with a STOP SEPSIS triage alert and clinical concern for sepsis. Patients enrolled were randomized to assessment of sepsis by clinical exam plus US (immediate) or clinical exam alone and then US 15 minutes later (delayed). Pre-test probability of sepsis were recorded prior to IVC US. Decision to initial sepsis protocol/pathway, pre-test and post-test probabilities were recorded before and after US. Primary outcomes included proportion of patients receiving antibiotics within 60 minutes based on intent-to treat principle; secondary outcomes include median total ED length of stay (EDLOS; triage time to disposition), time to secured vascular access, and vasopressor use. All outcomes between groups were compared by using a Pearson chi- squared test. The alpha level was set at .05 for all analyses, 95% CIs were calculated, and all comparisons were two tailed. Data analysis was performed with the use of SPSS 20.0 (IBM).

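### Protocol and SAP disagree on which endpoints are primary and on the sample size in both cohorts, and the available text does not say which document governs

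*Protocol*

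**What the plan says.** **Sepsis endpoints.** Protocol 5e names four primaries: "Secured second vascular access point- type (IO, second IV, CV access) within 15 min of physician evaluation"; "Inotrope/Vasopressor use"; antibiotics within 60 minutes; and a saline bolus completed within 60 minutes. The SAP's Sepsis Statistical Plan states "Primary outcomes included proportion of patients receiving antibiotics within 60 minutes based on intent-to treat principle" and puts "time to secured vascular access, and vasopressor use" among the secondary outcomes. It does not mention the bolus.

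**Gastroenteritis endpoints.** Protocol 5e names three primaries: oral versus intravenous rehydration, "Total amount of fluids given (ml amount", and "Total ED length of stay from triage time to disposition time (order to admit/discharge". The SAP's Gastroenteritis Statistical Plan states "Primary outcomes included IV versus PO rehydration based on intent-to treat principle; secondary outcomes included median total ED length of stay". It does not mention total fluid.

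**Sample size.** Protocol 5c gives sepsis "82 per group or 164 total patients for a power of 80% and a type I error set at 5"%, starting from 58% compliance with sepsis target times. It gives gastroenteritis 200 per group (400 in total), using a formula for a continuous time outcome. The SAP gives 200 patients for each cohort, each for a 15-point absolute difference with more than 80% power at two-sided 0.05. It states no baseline rate and does not say whether 200 is a total or per group. The SAP's sepsis sample-size paragraph stands at the end of its gastroenteritis section.

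**The concern.** The primary endpoint and the sample size fix what a trial may claim. Here both differ between two current documents, and the available text neither ranks the documents nor explains the change. A significant result on vasopressor use or ED length of stay could be reported as a primary success by citing the protocol, or treated as secondary by citing the SAP. The choice could be made after the data are seen.

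The sizing rests on different outcomes too. The protocol sizes gastroenteritis on time, and its only time primary in that cohort is ED length of stay, which the SAP makes secondary. Whether the SAP's power claim is true depends on a reading of 200 that the SAP leaves open.

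**Working it through.** **1. Endpoint status, side by side**

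| Cohort | Protocol 5e primary | Status in SAP |
|---|---|---|
| Sepsis | Second vascular access within 15 min | Secondary, redefined as time to secured access |
| Sepsis | Inotrope/vasopressor use | Secondary (vasopressor use) |
| Sepsis | Antibiotic within 60 min | Primary |
| Sepsis | Saline bolus within 60 min | Not mentioned |
| Gastroenteritis | Oral vs IV rehydration | Primary |
| Gastroenteritis | Total fluid | Not mentioned |
| Gastroenteritis | ED length of stay | Secondary |

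One primary per cohort is common to both documents.

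**2. Sample size under each reading of the SAP's 200**

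| Cohort | Protocol | SAP, 200 = total | SAP, 200 = per group |
|---|---|---|---|
| Sepsis | 164 | 200 (conflict) | 400 (conflict) |
| Gastroenteritis | 400 | 200 (conflict) | 400 (agrees) |

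**3. Reproducing the protocol's figures**

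Sepsis: m = 7.9 × [π₁(1−π₁) + π₂(1−π₂)] / (π₁−π₂)², with π₁ = 0.58. The effect is not stated, so it has to be inferred.
- +20 points: 7.9 × (0.58×0.42 + 0.78×0.22) / 0.20² = 7.9 × 0.4152 / 0.04 = 82.0 per group, the protocol's figure.
- +19 points gives 92.1 and +21 gives 73.4, so the protocol's 82 implies about 20 points.
- +15 points (the SAP's target): 7.9 × 0.4407 / 0.0225 = 154.7 per group.

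Gastroenteritis: c/δ² + 2 with c = 7.9 gives 792 if δ = 0.10 and 81 if δ² = 0.10. Neither yields 400. δ = 0.20 gives 199.5, which the formula labels a total and the protocol uses per group.

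**4. Power for the SAP's 15 points**

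Two-sided 0.05, pooled two-proportion normal test:
Power ≈ Φ{[Δ − 1.96√(2p̄(1−p̄)/n)] / √([p₁(1−p₁)+p₂(1−p₂)]/n)}.

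Example, 58% vs 73%, n = 100 per arm: the numerator is 0.15 − 1.96 × 0.0672 = 0.0182, the denominator is 0.0664, and Φ(0.275) = 60.8%.

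The SAP gives no baseline, so lower rates of 20–60% are assumed, with two more extreme pairs for contrast.

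| Rates | 82/arm | 100/arm | 200/arm |
|---|---|---|---|
| 10 v 25% | 71.9% | 80.2% | 97.9% |
| 20 v 35% | 57.7% | 66.3% | 92.2% |
| 30 v 45% | 51.0% | 59.2% | 87.5% |
| 42.5 v 57.5% (minimum) | 48.4% | 56.5% | 85.4% |
| 60 v 75% | 53.7% | 62.1% | 89.6% |
| 75 v 90% | 71.9% | 80.2% | 97.9% |

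For its own inferred contrast of 58% vs 78%, 82 per group gives 78.9%.

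Difference detectable with 80% power at lower rates of 20/30/40/50/60%:
- 82 per arm: 19.9/21.3/21.7/21.2/19.9 points
- 100 per arm: 17.9/19.3/19.7/19.3/18.2 points
- 200 per arm: 12.3/13.5/13.9/13.8/13.2 points

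**5. Recruitment (protocol 5d), before consent and exclusions**

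About 200 sepsis alerts are expected a year. Then 164/200 = 82% of a year's alerts, 200/200 = 100%, and 400/200 = 2 years. For gastroenteritis, 3,000 visits a year, assumed even, give 1,500 in six months, and 400/1,500 = 27%.

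**6. Safety interim (protocol 5i)**

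The stated 25% counts are 40 and 100. 25% of 164 is 41 and of 400 is 100, but 25% of 200 is 50.

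**The case against.** The case for narrowing the point has several parts.

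- **Missing text.** Part of the SAP was not available for this review and may give its date or status. That limits the statement about which document governs to the available text. The contradictions themselves remain.
- **Loose wording.** The SAP says its primary outcomes included the named one, which need not be exhaustive. For total fluid and the bolus, silence is weaker evidence than an express change. For ED length of stay, vasopressor use and vascular access, the SAP says secondary outright.
- **Effect sizes.** The protocol's 20 points is inferred, and its 58% is overall compliance with target times, not the antibiotic rate. Twenty against 15 points is therefore a difference of basis, not a contradiction in itself. This stands.
- **Power.** The shortfall needs 200 to be a total and a mid-range baseline. At a lower rate of about 10% or less, or 75% or more, 100 per arm reaches 80%. The firm defect is that the SAP states neither the baseline nor the meaning of 200.
- **Recruitment.** The 27% is soft: eligibility also requires a judgement that IV fluids would help, some patients qualify through diarrhoea alone, and the protocol itself cites seasonality. It does not show that 400 is easy to reach.
- **Remedy.** Several primaries with a multiplicity rule would also reconcile the documents. One primary per cohort is simpler because both documents already agree on it.

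**Conclusion.** The concern holds. Three of four sepsis primaries and two of three gastroenteritis primaries lose that status or go unmentioned in the SAP. The sepsis N conflicts under either reading of 200; the gastroenteritis N conflicts if 200 is a total. This must be fixed, because the trial's primary claims are not settled in advance.

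The endpoint and N conflicts rest on no assumption. The power statement does: if 200 is a total and the lower rate is 20–60%, power for 15 points is about 56–66%, and the difference detectable with 80% power is about 18–20 points. Combining the protocol's 164 with the SAP's 15 points would give about 48–58%.

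**What to change.** - **Endpoints.** Name the same single primary per cohort in both documents: antibiotics within 60 minutes, and IV versus oral rehydration. List the protocol's other primaries as secondary in both, with one definition of the vascular-access outcome.
- **Timing.** Add a dated statement of when and why the list was narrowed, confirming that this was done without knowledge of outcome data. If that cannot be stated, report the protocol 5e list as prespecified and the narrowing as post hoc.
- **Sample size.** For each cohort give one N (total and per group), the assumed baseline rate for that primary, the target difference and the power delivered.
  - Sepsis: keep a planned N and restate its power. At 80% power and lower rates of 20–60%, 164 supports about 20–22 points and 200 in total about 18–20.
  - Gastroenteritis: keep 400 (200 per group), justified by the SAP's 15-point target, since the protocol's formula does not yield it. If 200 in total is kept instead, restate the power.
- **Interim.** Restate the 25% counts in protocol 5i if N changes.

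**Cost.** Wording in protocol 5c, 5e and possibly 5i, and in both SAP sections. Keeping 164 and 400 adds no patients to the protocol's plan. Choosing 200 in total for sepsis adds 36 (200 − 164) and would need every alert expected in the 12-month enrolment period. If the SAP's gastroenteritis 200 was a total, 400 is 200 more than the SAP. The demoted endpoints can no longer be claimed as primary successes, and the stated power may look less favourable.

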All patients, regardless of age or gender, who present to the Emergency Department who trigger triage STOP SEPSIS ALERT (based on triage vital signs and chief complaint), vomiting requiring zofran or diarrhea with concern for dehydration/hypovolemia , whom the treating physician believes would benefit from intravenous fluids will be eligible for inclusion into this study. The “treating physician” refers to one of the Pediatric Emergency Medicine attendings or fellows, all of whom are listed as co-investigators on the application form submitted with this protocol. Only if and when a patient or parent expresses interest in participating in the study, the Attending or Fellow caring for the patient will determine if the patient is eligible. If the patient is eligible, and has no criteria that would exclude them from the study, written informed consent will be obtained from the guardian and assent will be obtained in children \geq 7 years old. The patient will be enrolled in the study and randomized to either the immediate ultrasonography group (US of the IVC first with before the clinician fully assesses the patient and places rehydration orders) or the control group (Ultrasonography at 15 minutes into the assessment and management of the patient).

	Protocol Name:	Randomized Controlled Trial of Inferior Vena Cava Ultrasonography in the Management and Disposition of Pediatric Patients Undergoing Evaluation for Sepsis and Dehydration
	Principal Investigator:	[name] [contact] [contact] or [contact]
	Primary Contact Name/Contact Info:	[name] [contact]
	Date Revised:	2/10/2015
	Study Number:	IF1733382

b) Inclusion and Exclusion Criteria

Inclusion criteria for enrollment in study:

All patients, regardless of age or gender, who present to the Emergency Department who:

- A. Trigger triage STOP SEPSIS ALERT (based on triage vital signs and chief complaint)
And/OR
- B. Present with vomiting requiring Zofran
And/OR
- C. Present with diarrhea with concern for dehydration/hypovolemia

whom the treating physician believes would benefit from intravenous fluids will be eligible for inclusion into this study.

Exclusion criteria for enrollment in study:

- (1) Unstable patients with life-threatening injuries who require ongoing resuscitation.
- (2) Patient undergoing traumatic resuscitation

c) Number of Subjects

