upon arrival and clinician evaluation. Those subjects randomized to the control arm will undergo IVC ultrasound after a timed 15 minute delay. The IVC will be scanned in both longitudinal and transverse planes. All study clinicians will undergo brief 20 minute standardized training session to review which images to obtain.. Still and dynamic images will be recorded and saved. Imaging procedure involves a credentialed ultrasound clinician using an ultrasound machine to visualize the inferior vena cava in order to assess the collapsibility and respiratory variation. This vessel is visualized by placing the ultrasound probe on the subxiphoid area of the abdomen using transducer gel. Images will be obtained in two axes (transverse and sagittal). Images/video will be recorded and stored using a unique study subject number to assure that health information remains confidential and de-identified. Treatment and management decisions will be at the discretion of the treating clinician. The enrolling clinician will be responsible for obtaining consent, randomization and completing the data collection forms. As indicated by the study inclusion criteria, all participants who have triggered the electronic Severe Stop Sepsis notification or have clinically suspected dehydration due gastroenteritis or vomiting will be screened and consented by the enrolling clinician. Given the published data that suggests inferior vena cava ultrasound may help clinicians more effectively and efficiently treat sepsis and dehydration, the main objective of this study is to see if it can reliably improve outcomes as well as improve compliance with targeted treatment goals. We believe that clinical care of subjects who undergo Inferior vena cava US is unlikely to be altered in a negative way.

g) Specimen Banking

Not applicable

h) Data Management and Confidentiality

During the process of data collection, patient identifiers will be collected (first and last name, MR#, age, birth date, date of visit. This identifying information is necessary for US will be located on only 1 form. This form will be kept in a locked file cabinet in a locked office remaining on the medical campus of Mount Sinai Hospital at all times.

Data forms will be kept in a secure locked file. HIPAA-sensitive Personal Health Information (PHI) will not be reused or disclosed to any other person or entity, except as required by regulation and law or for authorized oversight of the research project.

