Potential subjects will be approached in the privacy of the ED exam room, in which all personal, private, and sensitive information will be kept confidential as during any

 Mount Sinai	Protocol Title:	Randomized Controlled Trial of Inferior Vena Cava Ultrasonography in the Management and Disposition of Pediatric Patients Undergoing Evaluation for Sepsis and Dehydration
	Principal Investigator Name/Contact Info:	[name] [contact] [contact] or [contact]
	Primary Contact Name/Contact Info	[name] [contact]
	Date Revised:	2/10/2015
	Study Number:	IF1733382

routine doctor-patient exchange. The subject can decline participation at any point in the study.

10) Economic Impact on Subjects

There is no additional cost to the patient nor to the hospital. There is no charge for the performed inferior vena cava US to the patient.

11) Payment to Subjects

none

12) Consent Process

Consent will be obtained either from the potential participant if age 18 years or greater or the parent/guardian of the potential participant aged less than 18 years. Consent will be obtained in a private setting in the examination room of the Emergency Department prior to performing the ultrasound. The person providing consent will be allowed to consider the request free of time constraints and sense of obligation or white coat pressure. They will be given the opportunity to review the consent document and discuss it with whomever they like. Assent will be obtained for all potential participants greater than or equal to age 7 years and will be documented on the last page of the child consent form.

13) Process to Document Consent in Writing

Written consent with a paper based form will use basic language that is easy to understand (5th grade level). To ensure that the subject understands, they will be asked to reiterate in their own words the purpose of the research, what they will need to do as participants in the study, and what the potential risks and alternatives are.

14) Vulnerable Populations

Protocol Title:	Randomized Controlled Trial of Inferior Vena Cava Ultrasonography in the Management and Disposition of Pediatric Patients Undergoing Evaluation for Sepsis and Dehydration
Principal Investigator Name/Contact Info:	[name] [contact] [contact] or [contact]
Primary Contact Name/Contact Info	[name] [contact]
Date Revised:	2/10/2015
Study Number:	IF1733382

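### Gastroenteritis length of stay runs from triage with no adjustment for the wait before randomisation: no bias, but probably lost power, by an amount the documents do not let us calculate

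*Protocol*

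**What the plan says.** Protocol section 5 e) lists three primary endpoints for the gastroenteritis/dehydration arm. One is "Total ED length of stay from triage time to disposition time (order to admit/discharge". The SAP, Gastroenteritis Statistical Plan, uses the same starting point but a different rank: "secondary outcomes included median total ED length of stay (EDLOS; triage time to disposition". It compares all outcomes with a Pearson chi-squared test and describes no covariate adjustment.

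Randomisation happens well after triage. Protocol section 5 a) sets the order:

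- The family shows interest and the physician then decides on eligibility: "Only if and when a patient or parent expresses interest in participating in the study, the Attending or Fellow caring for the patient will determine".
- Written consent follows, with assent from age 7.
- Allocation comes last: "The patient will be enrolled in the study and randomized to either the immediate ultrasonography group".

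Section 12 requires consent before the scan and sets no limit on how long it takes: "The person providing consent will be allowed to consider the request free of time constraints".

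The arms differ only from allocation onwards. Section 5 f) says of the controls: "Those subjects randomized to the control arm will undergo IVC ultrasound after a timed 15 minute delay".

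**The concern.** Each recorded stay is the sum of two parts: the interval from triage to randomisation, and the interval from randomisation to the disposition order. Only the second can respond to the timing of the scan. The first has the same expected length in both arms, so it adds nothing to the difference in mean stay, but its variation between patients enters the outcome. Unless that variation is offset by a negative correlation with the later stay, an unadjusted comparison is less precise than it need be.

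This matters most under the protocol, where stay is a primary endpoint and the gastroenteritis sample size in section 5 c) is built on a continuous time outcome with a 10% reduction as target.

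**Working it through.** **1. The plan's own figure.** Section 5 c) gives total = c/δ² + 2 with c = 7.9 for 80% power and a 10% effect, and states 200 per group, 400 in total. The formula gives:

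- δ = 0.10: 7.9/0.01 + 2 = 792
- δ² = 0.10: 7.9/0.10 + 2 = 81
- δ = 0.20: 7.9/0.04 + 2 = 199.5

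So 200 does not follow from a 10% effect. It matches only δ = 0.20, and then as a total, not per group. No mean or SD of stay is given, so the plan offers no usable baseline power. What follows takes 200 per group as the size and assumes 80% power when stay is timed from randomisation.

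**2. Set-up.** Let W be triage to randomisation, S randomisation to disposition order, and T = W + S the recorded stay. Let k = SD(W)/SD(S) and ρ = corr(W, S). Neither k nor ρ is in the documents; both are assumed. The arm difference in mean minutes is the same for T and S. The variance is

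Var(T) = Var(S) × (1 + k² + 2ρk).

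Var(T) exceeds Var(S) only if k² + 2ρk > 0, that is ρ > -k/2. At or below that value the triage clock loses nothing.

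**3. Effect giving 80% power from randomisation.** Two-sided 5%, 200 per group: d = √(2 × (1.96 + 0.8416)²/200) = 0.280 SD of S.

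**4. Power from triage.** Power = Φ((1.96 + 0.8416)/√(1 + k² + 2ρk) - 1.96). For example, k = 0.5 and ρ = 0 gives 2.8016/√1.25 - 1.96 = 0.546, so 70.7%.

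| ρ | k = 0.25 | k = 0.5 | k = 1 |
|---|---|---|---|
| +0.25 | 72.9% | 62.8% | 42.5% |
| 0 | 77.6% | 70.7% | 50.8% |
| -0.25 | 82.5% | 80.0% | 62.8% |
| -0.5 | 87.5% | 89.9% | 80.0% |

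At ρ = 0, restoring 80% would take 200 × 1.0625 = 212.5 (213), 200 × 1.25 = 250, or 200 × 2 = 400 per group.

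**5. The SAP's size.** The SAP has 200 patients in all. Taking 100 per group (equal allocation assumed) and the same d, power is 50.8% from randomisation. From triage at ρ = 0 it is 48.5%, 42.5% or 28.8% for k = 0.25, 0.5 or 1.

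**6. Keeping the triage clock and adjusting for W.** The residual variance of T given W is Var(S) × (1 - ρ²). At 200 per group, power is 80.0% at ρ = 0, 82.5% at ρ = ±0.25 and 89.9% at ρ = ±0.5. In large samples this is never below either unadjusted clock, whatever ρ is.

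Steps 2 to 6 concern mean stay in minutes. On the log scale the direction of the argument carries over, but these exact figures do not.

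**The case against.** **The endpoint is legitimate.** Total ED stay matters to families and to the department, and both documents time it the same way in this arm. That stands, and it is why the outcome should be kept. A reader might infer that the triage clock biases the comparison or must be replaced. The documents do not support either: the interval is balanced in expectation by randomisation, and adjustment recovers the precision without changing the endpoint.

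**The loss is not certain.** A reader might take the wait's variance as added in full. That is true only if wait and later stay are uncorrelated. If care begun during the wait shortens what follows, the loss can vanish or reverse, as the lower rows of the table show. The documents support neither a zero nor a negative correlation, so the loss is likely but conditional.

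**Moving the clock is not neutral for the SAP's summary.** The equal-difference argument holds for means. The SAP reports a median, and medians do not add, so a randomisation clock could change the reported contrast.

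**The SAP's primary outcome is untouched.** Its 200 patients are sized on a 15-point difference in oral versus intravenous rehydration. A chi-squared test cannot compare a time unless stay is cut into categories, so the SAP as written defines no power for stay. This limits the importance of the point. It does not remove it, because stay remains a protocol primary and correcting the test alone would leave the noise in place.

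**The interval may be short.** Section 5 f) describes the investigational scan as immediate on arrival and evaluation. But consent must come before the scan, so some variable interval remains.

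**Conclusion.** The point holds as one of efficiency. Gastroenteritis stay includes an interval before randomisation that allocation cannot affect, and neither document adjusts for it. There is no bias. An unadjusted comparison is likely to lose power unless ρ is at or below -k/2.

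The size cannot be derived from the documents. With zero correlation, 200 per group and 80% power from randomisation, the loss is about 2, 9 or 29 percentage points at k = 0.25, 0.5 or 1; k, ρ and the 80% starting point are all assumed. It would be wrong to read these as estimates for this trial. It would also be wrong to treat this as the main power problem for stay: the protocol's size does not follow from its 10% effect, the two documents disagree on 400 versus 200 patients, and the named test does not suit a time.

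**What to change.** - **Keep the outcome.** Leave triage-to-disposition stay as defined in protocol section 5 e) and in the SAP.
- **Record the randomisation time.** Neither document says it is captured, so add it to the data form, or take it from the randomisation application if that stores it. It must be the time of allocation. The time of the scan depends on arm and must not be used as the covariate.
- **Change the test.** In the SAP, Gastroenteritis Statistical Plan, take stay out of the blanket chi-squared sentence. State instead that stay will be compared between arms by a regression (for example on log stay) with terms for arm and the triage-to-randomisation interval, reporting the adjusted contrast with its 95% CI.
- **Report alongside.** Give unadjusted median stay by arm, the SD of the triage-to-randomisation interval, and stay from randomisation as a supportive analysis.

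The cost is one more timestamp and a model-based contrast to explain beside the medians. No patients are added and the endpoint is unchanged.
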